5.1. Overall Design

Study I9N-MC-FCAB (FCAB) is a Phase 2, multicenter, randomized, double-blind, placebo-controlled, parallel-group, outpatient study evaluating the efficacy and safety of LY3375880 SC 600 mg Q4W, 150 mg Q4W, and 50 mg Q4W as compared to placebo Q4W in adult subjects with moderate-to-severe AD. In addition, LY3375880 300mg Q4W will be evaluated in the maintenance period as described below.

The study duration will be up to 65 weeks over 4 study periods:

- Period 1: Screening Period lasting from 8 to 35 days prior to Week 0 (baseline, Visit 2).
- Period 2: Induction Period, lasting from Week 0 (baseline, Visit 2) through Week 16 (Visit 8).
- Period 3: Maintenance Period, lasting from Week 16 (Visit 8) through Week 52 (Visit 17, inclusive). At Week 16, the following will occur:
 - Responders (defined as having achieved a 50% reduction in the Eczema Area and Severity Index score [EASI-50] response, regardless of whether rescue therapy has been initiated) will undergo the following re-randomizations:
 - Subjects on any dose of LY3375880 will be re-randomized at a 2:1 ratio to either maintain their current regimen or to receive placebo until loss of response (not achieving a 25% reduction in the EASI score [EASI-25] at a scheduled visit), at which point they will restart their induction period regimen.
 - Subjects on placebo will continue receiving placebo until loss of response, at which point they will be reassigned to receive LY3375880 at 300 Q4W.
 - Nonresponders will undergo the following reassessments:
 - Subjects on 50 mg Q4W will be reassigned to 150 mg Q4W.
 - Subjects on 150 mg Q4W will be reassigned to 300 mg Q4W.
 - Subjects on 600 mg Q4W will remain on their current regimen.
 - Subjects on placebo will be reassigned to receive 300 mg Q4W.
 - Subjects with persistent disease activity, defined as not achieving EASI-25 for 3 consecutive scheduled maintenance period visits, not already on 600 mg Q4W will be reassigned to 600 mg Q4W for the remainder of the study.
- Period 4: Post-Treatment Follow-Up Period, spanning approximately 8 weeks from Week 52 (after Visit 17) to Week 60 (Visit 801).

Rescue therapy is permitted starting at Week 8 for subjects who do not achieve an EASI-25 response. Refer to Section [7.7.3](#) for details.

Treatment Arms and Duration:

[figure not shown]

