Approximately 200 subjects will be randomized 1:1:1:1 at Week 0 to 1 of 4 treatment groups in the induction period: placebo SC (Q4W), LY3375880 SC 600 mg (Q4W), LY3375880 150 mg (Q4W), or LY3375880 50 mg (Q4W). The study duration will be up to 65 weeks (Screening

Period: Up to 5 weeks; Induction Period: 16 weeks; Maintenance Period: 36 weeks; Follow-up Period: 8 weeks).

Subjects will be stratified at randomization according to disease severity (IGA [3 versus 4]) and geographic region (Japan versus non-Japan).

All procedures to be conducted during the study, including timing of all procedures, are indicated in the Schedule of Activities (Section 2). [Appendix 2](#) describes collection of laboratory samples with the list of specific laboratory tests that will be performed for this study. Study governance considerations are described in detail in [Appendix 3](#).

[Figure FCAB.1](#) illustrates the study design.

Abbreviations: R = Responders.

Response to study drug is defined as achieving an EASI-50. At Week 16, responders on LY3375880 will be re-randomized to either maintain current dosing regimen or placebo until disease recurrence (EASI-25). Placebo responders will continue on placebo until disease recurrence.

NR = Nonresponders. At Week 16, nonresponders will be reassigned to 600 mg Q4W, 300mg Q4W, or 150 mg Q4W depending on treatment group.

Note: Subjects with persistent disease activity, defined as not achieving EASI-25 for 3 consecutive scheduled maintenance period visits, not already on 600 mg Q4W will be reassigned to 600 mg Q4W for the remainder of the study.

Figure FCAB.1. Study design for Study I9N-MC-FCAB.

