## 4. Study Design

### 4.1. Summary of Study Design

Study I9N-MC-FCAB(b) (FCAB) is a Phase 2, multicenter, randomized, double-blind, placebo-controlled, parallel-group, outpatient study evaluating the efficacy and safety of LY3375880 subcutaneous (SC) 600 mg every 4 weeks (Q4W), 150 mg Q4W, and 50 mg Q4W as compared to placebo Q4W in adult subjects with moderate-to-severe AD. In addition, LY3375880 300mg Q4W will be evaluated during the maintenance period. The study duration will be up to 65 weeks over 4 study periods:

[figure not shown]
- Period 1: Screening Period lasting from 8 to 35 days prior to Week 0 (baseline, Visit 2).
- Period 2: Induction Period, lasting from Week 0 (baseline, Visit 2) through Week 16 (Visit 8), inclusive.
  - An internal assessment committee will conduct an unblinded interim analysis of efficacy safety data when approximately 40%-60% of patients complete Week 16 (Visit 8). This interim analysis will be conducted for internal decision making to trigger planning activities for future studies associated with LY3375880.
- Period 3: Maintenance Period, lasting from Week 20 (Visit 9) through Week 52 (Visit 17), inclusive. At Week 20, the following will occur:
  - Responders (defined as having achieved a 50% reduction in the Eczema Area and Severity Index score [EASI-50] response, regardless of whether rescue therapy has been initiated) will undergo the following re-randomizations:
    - Subjects on any dose of LY3375880 will be re-randomized at a 2:1 ratio to either maintain their current regimen or to receive placebo until loss of response (not achieving a 25% reduction in the EASI score [EASI-25] at a scheduled visit), at which point they will restart their induction period regimen.
    - Subjects on placebo will continue receiving placebo until loss of response, at which point they will receive LY3375880 300 mg Q4W.
  - Nonresponders will undergo the following re-randomizations/reassignments:
    - Subjects on 50 mg Q4W will be reassigned to 150 mg Q4W
    - Subjects on 150 mg Q4W will be reassigned to 600 mg Q4W
    - Subjects on 600 mg Q4W will remain on their current regimen
    - Subjects on placebo will receive LY3375880 300 mg Q4W.
  - Subjects with persistent disease activity defined as not achieving EASI-25 for 3 consecutive maintenance period visits, or 8 maintenance period weeks (whichever is longer) not already on 600 mg Q4W will be reassigned to 600 mg Q4W for the remainder of the study.

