### **5.2.1. Analysis Populations**

**Enrolled population:** The enrolled population is defined as all participants who sign informed consent.

**Intent-to-treat (ITT) population:** The ITT population analysis set is defined as all randomized patients, even if the patient does not take the assigned treatment, does not receive the correct treatment, or otherwise does not follow the protocol.

**Per-Protocol (PPS) population:** The PPS populations is defined as all randomized patients who do not commit an Important Protocol Deviation (IPD) that could potentially compromise efficacy results.

**Safety population:** The safety population is defined as all randomized patients who receive at least 1 dose of their assigned double-blind study treatment..

**Maintenance Period Population:** All ITT patients who received at least one dose of study treatment and have entered the maintenance period at Week 16 (Visit 8).

Unless otherwise specified, the efficacy and health outcome analyses will be conducted on the ITT population (Gillings and Koch 1991), which seeks to preserve the benefits of randomization and avoid the issue of selection bias. Patients will be analyzed according to the treatment to which they were randomized.

Safety analyses will be done on the safety population. Patients will be analyzed according to the dosing regimen to which they were assigned. Analyses of the safety endpoints, many of which are incidence based, will include all patients in the safety population, unless specifically stated otherwise.

In the rare situation where a patient is Lost to Follow-up at the first postbaseline visit, but some safety data exists (eg, unscheduled laboratory assessments) after first dose of study drug, a listing of the data or a patient profile will be provided.

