|   | • Proportion of patients achieving IGA [0]  |                                 | Maintenance                | LY3375880 600-mg or LY3375880 300-mg or LY3375880 150-mg or LY3375880 50-mg vs PBO; Week 52 | Secondary analysis   |
|   | • Proportion of patients achieving IGA [0]  | Logistic regression using NRI   | ITT                        | LY3375880 600-mg or LY3375880 150-mg or LY3375880 50-mg vs PBO; Week 16                     | Secondary analysis   |
| Eczema Area and Severity Index (EASI)                   | • EASI score
• Change from baseline in EASI score
• Percent change from baseline in EASI score                                | MMRM                            | ITT; PPS                   | LY3375880 600-mg or LY3375880 150-mg or LY3375880 50-mg vs PBO; Week 16                     | Secondary analysis   |
|   | • Proportion of patients achieving EASI50
• Proportion of patients achieving EASI75
• Proportion of patients achieving EASI90 | Logistic regression using NRI   | ITT; PPS                   | LY3375880 600-mg or LY3375880 150-mg or LY3375880 50-mg vs PBO; Week 16                     | Secondary analysis   |
| Body Surface Area (BSA) Affected by AD                  | • BSA score
• Change from baseline in BSA score  | MMRM                            | ITT                        | LY3375880 600-mg or LY3375880 150-mg or LY3375880 50-mg vs PBO; Week 16                     | Exploratory analysis |
| SCORing Atopic Dermatitis (SCORAD)                      | • SCORAD score
• Change from baseline in SCORAD score
• Percent change from baseline in SCORAD score                          | MMRM                            | ITT                        | LY3375880 600-mg or LY3375880 150-mg or LY3375880 50-mg vs PBO; Week 16                     | Secondary analysis   |
|   | • Proportion of patients achieving SCORAD75
• Proportion of patients achieving SCORAD90  | Logistic regression using NRI   | ITT; PPS                   | LY3375880 600-mg or LY3375880 150-mg or LY3375880 50-mg vs PBO; Week 16                     | Secondary analysis   |

| Measure                                | Variable   | Analysis Method (Section 5.2.3) | Population (Section 5.2.1)                              | Comparison/Time Point   | Analysis Type        |
|--|--|---------------------------------|---|---|----------------------|

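### The SAP's Week 52 comparison of 300 mg with placebo has no randomised basis: by Week 16 assignment it sets EASI-50 nonresponders against EASI-50 responders

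*SAP*

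**What the plan says.** The Week 52 row for IGA in SAP Table FCAB.5.2 (Section 5.11) names the Maintenance population, labels the analysis secondary, and gives the comparison as "LY3375880 600-mg or LY3375880 300-mg or LY3375880 150-mg or LY3375880 50-mg vs PBO; Week 52". It does not define the groups. The Maintenance population in SAP 5.2.1 states who is included, not how they are grouped. The only grouping rule for efficacy in that section is "Patients will be analyzed according to the treatment to which they were randomized".

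Protocol 5.1 sets the routes to each maintenance regimen:

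- **Week 0:** "Approximately 200 subjects will be randomized 1:1:1:1 at Week 0 to 1 of 4 treatment groups in the induction period". The groups are placebo, 50, 150 and 600 mg.
- **Active responders (EASI-50) at Week 16:** "Subjects on any dose of LY3375880 will be re-randomized at a 2:1 ratio to either maintain their current regimen or to receive placebo".
- **Placebo responders:** "Subjects on placebo will continue receiving placebo until loss of response, at which point they will be reassigned to receive LY3375880 at 300 Q4W".
- **Placebo nonresponders:** "Subjects on placebo will be reassigned to receive 300 mg Q4W".
- **150 mg nonresponders:** "Subjects on 150 mg Q4W will be reassigned to 300 mg Q4W". SAP 4.1 differs: "Subjects on 150 mg Q4W will be reassigned to 600 mg Q4W".

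On method, Protocol 10.2.1.2 limits maintenance analyses to descriptive statistics, with a proportion and 95% CI by treatment. Protocol 10.2.3.2 nevertheless lists IGA 0 or 1 at Week 52 among the endpoints for logistic regression, and SAP 5.2.3 makes logistic regression the main method for categorical efficacy variables, with region, baseline IGA and treatment in the model.

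**The concern.** The row presents 300 mg against placebo as a dose comparison. The as-randomised rule produces no 300 mg group, so the row can be run only with groups shaped by Week 16 outcome. Subjects reach 300 mg because they did not respond (or, later, lost response). Subjects stay on or move to placebo because they did respond.

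If the row is run as a test, an inert 300 mg dose can appear worse than placebo and a real effect can be masked. If it is only descriptive, the label still misdescribes a responder-versus-nonresponder difference. Protocol 5.4 says the 300 mg data will support exposure-response modelling and dose selection, so a misleading result could be noticed. No passage makes this pairwise contrast a decision rule.

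**Working it through.** **The plan's own figure.** The documents give power only for Week 16. Exact enumeration of the two-sided Fisher test with 50 per arm, 36% versus 8%, alpha 0.05, gives 91.4%, which agrees with the stated minimum of 90%. It does not bear on Week 52.

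**Composition by Week 16 assignment (Protocol 5.1).** Let *e* be the EASI-50 rate, assumed equal in all arms (no drug effect), with 50 per arm and no dropout.

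- Placebo group = 50*e* placebo responders + (1/3)(150*e*) active responders re-randomised to placebo = 100*e*. All are responders.
- 300 mg group = 50(1 − *e*) from placebo + 50(1 − *e*) from 150 mg = 100(1 − *e*). All are nonresponders.
- Randomised to 300 mg: 0.

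The documents give no EASI-50 rates. For *e* assumed at 25 to 45%, placebo has 25 to 45 subjects and 300 mg has 75 to 55. Treatment and prior response coincide exactly. Adding Week 16 response to the model would not help, because neither group contains both kinds of subject.

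**Size of the spurious gap with no drug effect.** Assume latent Week 16 and Week 52 outcomes are bivariate normal with correlation *r*, and overall Week 52 response is *q*. With *J* = Φ₂(Φ⁻¹(*e*), Φ⁻¹(*q*); *r*):

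- response in Week 16 responders = *J*/*e*
- response in nonresponders = (*q* − *J*)/(1 − *e*)

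Results for *r* from 0.3 to 0.7 and *e* from 25 to 45%:

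| Overall Week 52 response (assumed) | Placebo minus 300 mg, points | Fisher rejection at 0.05 |
|---|---|---|
| 8% | 7.2 to 23.2 | 21 to 90% |
| 4% | 4.1 to 13.1 | 11 to 65% |
| 2% | 2.3 to 7.1 | 2 to 34% |

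At 8%, the low end is 12.0% versus 4.8% (*e* = 45%, *r* = 0.3) and the high end is 25.4% versus 2.2% (*e* = 25%, *r* = 0.7). The 8% is the documents' Week 16 placebo rate for IGA 0 or 1 with at least a 2-point improvement, carried to Week 52 as an assumption. The 2% row is an assumed rate for IGA 0. Rejection rates come from 2,000 simulated trials per scenario and are essentially all against the drug.

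**Other doses, same setting at 8%.** The 150 and 600 mg groups mix retained responders with nonresponders and are rejected in 7 to 55% of trials. The 50 mg group, all retained responders, is rejected in 1 to 3%. The re-randomised contrast of continued drug versus placebo is rejected in 2 to 3%.

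**Grouping by treatment at Week 52.** Loss-of-response switching and the move to 600 mg were simulated with EASI-25 assumed at 45 to 80%. The confounding is no longer total, because 300 mg gains placebo responders who lost response, but placebo keeps only sustained responders. At 8% the gap is 12 to 37 points and 300 mg is rejected in 10 to 84% of trials. At 2% the gap is 4 to 13 points, with rejection in 6 to 26%. All rejections are against the drug.

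**Effect of the reassignment conflict** (*e* = 35%, *r* = 0.5, 8%; groups by Week 16 assignment). Using SAP 4.1 instead of Protocol 5.1, the mean 300 mg group falls from 65 to 33 subjects and its rejection rate from 57.5% to 31.8%. The mean 600 mg group rises from 44 to 77 and its rejection rate from 22.2% to 40.8%.

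**The case against.** The strongest reply is that no test may be intended. Protocol 10.2.1.2 allows only descriptive maintenance statistics. The objective in SAP 3.2 words its comparison for Week 16 alone, although IGA 0 or 1 at Week 52 is listed under it. The method cell of the row is blank in the text available to us, possibly an extraction artefact. This makes testing unresolved rather than planned. It does not rescue the row, which still prints a comparison with placebo and a secondary label, while Protocol 10.2.3.2 assigns logistic regression.

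Second, the rejection rates above use Fisher's test, which SAP 5.2.3 makes secondary to the logistic p-value. The covariate-adjusted model was not run. An unadjusted two-group Wald test, counting tables with an empty cell as non-rejections, rejects less often at 8%: about 14 to 73%. The shortfall is mostly due to empty cells and does not make the contrast valid.

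Third, the EASI rates, correlation and Week 52 rates are assumed, and dropout, rescue and nonresponder imputation are ignored. When groups follow treatment at Week 52, the mean placebo group can be as small as 2 subjects. The percentages are illustrations.

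Fourth, outcome-dependent grouping is forced only for 300 mg. The other doses could be grouped by Week 0 arm. That is correct, but the row does not say so. Such a grouping would compare strategies, since every placebo nonresponder moves to 300 mg. In the simulation, 62 to 98% of the placebo arm is on active drug by Week 52, including 55 to 75% from Week 16 nonresponse alone.

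**Conclusion.** The concern holds. The 300 mg comparison cannot be formed as randomised, and when formed by Week 16 assignment it is completely confounded with response. That conclusion follows from the assignment rules alone. The direction of the bias needs only a positive association between Week 16 and Week 52 outcomes. Its size depends on the assumptions above: with no drug effect and 8% overall response, 7 to 23 points against 300 mg by Week 16 assignment and 12 to 37 points by treatment at Week 52. The 150 and 600 mg contrasts are partly affected under either grouping. The harm is a misleading secondary result, which should be fixed. The Week 16 primary and secondary analyses are untouched.

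**What to change.** 1. Delete from the Week 52 row the 300 mg comparison with placebo and any other placebo contrast between groups defined by maintenance treatment.
2. Report IGA 0 or 1 at Week 52 as proportions with 95% CI by treatment sequence (Week 0 arm, Week 16 response, maintenance regimen). This fits Protocol 10.2.1.2. Align the Week 52 bullet in Protocol 10.2.3.2.
3. If a Week 52 placebo contrast is kept, use continued drug versus placebo among re-randomised active responders, analysed as re-randomised, pooled over or stratified by dose, as an estimate with CI. State in advance how subjects who restart active drug after loss of response are counted. Keeping this contrast also gives the Week 52 part of the protocol's comparative objective an analysis; otherwise that objective's wording needs aligning.
4. A comparison by Week 0 arm may be added only if labelled a comparison of treatment strategies that does not estimate drug versus placebo at Week 52.
5. Check the row's method cell and variable against the original table. The variable reads IGA 0 in our text, whereas both objective tables name IGA 0 or 1; align it with those.
6. Reconcile Protocol 5.1 and SAP 4.1 on 150 mg nonresponders, since this sets membership of the 300 and 600 mg groups.

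The cost is one SAP row, wording that defines the groups, and one protocol bullet, plus the objective's wording if no Week 52 contrast is kept. Formal tests of maintenance dose against placebo are lost, and the randomised replacement is imprecise. At EASI-50 of 25 to 45%, it has about 25 to 45 versus 13 to 23 subjects pooled over doses. The Newcombe-Wilson 95% CI half-width is then about 28 to 21 points if 25% respond in both groups, and about 43 to 35 points per dose. Protocol 10.2.1 lets an analysis change that is not a principal feature be described in the clinical study report. That rule covers analysis methods only, so the reassignment conflict must be resolved separately.

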### **5.11.1. Primary Outcome and Methodology**

The validated Investigator's Global Assessment for AD (IGA) uses the clinical characteristics of erythema, papulation/induration, oozing/crusting and lichenification to produce a single-item score ranging from 0 to 4. The primary analysis of the study is to test the hypotheses that LY3375880 600-mg, LY3375880 150-mg, or LY3375880 50-mg is superior to placebo when evaluating the proportion of patients achieving IGA of 0 or 1 with a  $\geq 2$ -point improvement from baseline at Week 16 using the ITT population. A logistic regression analysis as described in Section 5.2.3 will be used for the comparisons. The odds ratio, the corresponding 95% CIs and p-value, as well as the treatment differences and the corresponding 95% CIs, will be reported. Missing data will be imputed using the NRI method described in Section 5.4.1.

### **5.11.2. Secondary and Exploratory Efficacy and Health Outcomes Analyses**

The secondary and exploratory efficacy analyses, as well as the health outcomes analyses, are detailed in Table FCAB.5.1. There will be no adjustment for multiple comparisons for other analyses.

## **5.12. Bioanalytical and Pharmacokinetic/Pharmacodynamic Methods**

Pharmacokinetic, Pharmacodynamic and Biomarker analyses to address secondary and exploratory objectives of this study will be described by Lilly in separate PK/PD and Biomarker analysis plans.

## **5.13. Safety Analyses**

The general methods used to summarize safety data, including the definition of baseline value are described in Section 5.2.2.

Safety analyses will include data after rescue, unless otherwise stated, and patients will be analyzed according to the investigational product to which they were randomized at Week 0 (Visit 2). Additional analyses may be conducted using data after rescue to systemic therapy for some safety topics such as systemic treatment-emergent adverse events (TEAEs), and serious adverse events (SAEs). Safety analyses will take place using the safety population defined in Section 5.2.1.

Safety topics that will be addressed include the following: AEs, clinical laboratory evaluations, vital signs and physical characteristics, Columbia Suicide Severity Rating Scale (C-SSRS), the Self-Harm Supplement Form, safety in special groups and circumstances, including adverse events of special interest (AESI) (see Section 5.13.5), and investigational product interruptions.

Unless otherwise specified, by-visit summaries will include planned on-treatment visits. For tables that summarize events (such as AEs, categorical lab abnormalities, shift to maximum value), post-last dose follow-up data will be included. Follow-up data is defined as all data occurring up to 30 days (planned maximum follow-up time) after last dose of treatment including rescue, regardless of study period except for deaths and malignancies. For deaths and

malignancies, all available follow-up data up to the end of the study will be included. Listings will include all safety data.

For selected safety assessments, descriptive statistics may be presented for the last measure observed during post-treatment follow-up (up to 30 days after the last dose of treatment including rescue, regardless of study period).

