- Period 4: Post-Treatment Follow-Up Period, spanning approximately 8 weeks from Week 52 (Visit 17) to Week 60 (Visit 801).

Approximately 200 subjects will be randomized 1:1:1:1 at Week 0 to 1 of 4 treatment groups: placebo SC (Q4W), LY3375880 SC 600 mg (Q4W), LY3375880 150 mg (Q4W), or LY3375880

50 mg (Q4W). The study duration will be up to 65 weeks (Screening Period: Up to 5 weeks; Induction Period: 16 weeks; Maintenance Period: 36 weeks; Follow-up Period: 8 weeks).

Subjects will be stratified at randomization according to disease severity (IGA [3 versus 4]) and geographic region (Japan versus Rest of World).

Figure FCAB.4.1 illustrates the study design. The blinding procedure is described in the Protocol.

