### **5.2.2. Definition of Baseline and Postbaseline Measures**

The baseline value for the efficacy and health outcomes for the Induction and Maintenance Periods is defined as the last non-missing measurement on or prior to the date of first study drug administration (expected at Week 0, Visit 2). The baseline value for the daily diary assessments (Itch NRS, Skin Pain NRS) is defined as the average of the non-missing assessments in the last 7 days prior to the date of first study drug administration (expected at Week 0, Visit 2). Criteria for derivation of the weekly average requires that there must be at least 4 non-missing measurements in the 7 days indicated, otherwise, an expanded window of 14 days prior to first study drug administration, if available, may be utilized in order to obtain the most recent 4 non-missing measurements prior to first study drug administration (ie, Day -14 to Day -1). If there are not at least 4 non-missing assessments collected prior to the date of first study drug

administration using the aforementioned method, then the baseline will be designated as missing. Other definitions of baseline value, such as the last measurement on or prior to rescue, may be used to conduct additional supporting analyses.

Postbaseline measurements are collected after study drug administration through Week 60 (Visit 801) or early discontinuation visit. For data collected in the electronic Clinical Outcomes Assessment (eCOA) tablet (including Patient-Reported Outcomes [PRO] and Clinician-Reported Outcomes [ClinRO]) and related to efficacy assessments, unscheduled postbaseline visits that fall within the visit windows defined by Lilly will be summarized in the by-visit analyses if there is no scheduled visit available. That is, a  $\pm 2$  day window is applied to Visit 3 (Week 1), Visit 4 (Week 2), and Visit 5 (Week 4), and a  $\pm 4$  day window is applied to Visit 6 (Week 8), Visit 7 (Week 12), and Visit 8 (Week 16), as well as to every visit in the Maintenance Period. If there is more than 1 unscheduled visit within the defined visit window and no scheduled visit is available, the unscheduled visit closest to the scheduled visit date will be used.

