### **5.13.2. Adverse Events**

Adverse events are recorded in the eCRFs. Each AE will be coded to system organ class (SOC) and preferred term (PT) using the Medical Dictionary for Regulatory Activities (MedDRA) version that is current at the time of database lock. Severity of AEs is recorded as mild, moderate, or severe.

A TEAE is defined as an event that either first occurred or worsened in severity after the first dose of study treatment and on or prior to the last visit date during the analysis period. The analysis period is defined as the treatment period plus 30 days off-drug follow-up time, except for deaths and malignancies for which the analysis period includes the treatment period and off-drug follow-up time.

Adverse events are classified based upon the MedDRA PT. The MedDRA Lowest Level Term (LLT) will be used in defining which events are treatment-emergent. The maximum severity for each LLT during the baseline period up to first dose of the study medication will be used as baseline. If an event with missing severity is preexisting during the baseline period, and persists during the treatment period, then the baseline severity will be considered mild for determining TEAE (that is, the event is treatment-emergent if the severity is coded moderate or severe postbaseline and not treatment-emergent if the severity is coded mild postbaseline). If an event occurring postbaseline has a missing severity rating, then the event is considered treatment-emergent. The day and time for events where onset is on the day of the first dose of study treatment will both be used to distinguish between pretreatment and posttreatment in order to derive treatment-emergence. Should there be insufficient data for AE start date to make this comparison (for example, the AE start year is the same as the treatment start year, but the AE start month and day are missing), the AE will be considered treatment-emergent.

In an overview table, the number and percentage of subjects who experienced a TEAE or serious adverse event (SAE), died due to an AE, or discontinued from study due to an AE will be summarized by treatment.

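### SAP 5.13 groups safety data by Week 0 product without limiting this to induction and defines no maintenance or 300-mg safety group; its 30-day follow-up maximum also conflicts with the planned 8 weeks

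*SAP*

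**What the plan says.** **Grouping.** SAP 5.13 states that "patients will be analyzed according to the investigational product to which they were randomized at Week 0 (Visit 2". The clause follows one about data after rescue, so a narrower intent is possible, but none is written. SAP 5.2.1 uses different words: safety patients are analyzed by the regimen to which they were assigned. Protocol 10.1 and 10.2.1 say the group to which subjects were randomized. None of these mentions the later re-randomization or reassignment.

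Maintenance safety output is nevertheless planned: exposure by treatment group (SAP 5.13.1), laboratory shift displays for both periods (5.13.3) and creatinine shift tables for both periods (5.13.6.2). SAP 5.2.2.2 gives a maintenance safety baseline. The adverse event tables in 5.13.2 state no period split. A 300-mg group appears in SAP Table FCAB.5.2 for Week 52 efficacy, but nowhere in 5.13. Protocol 5.4 gives safety data at 300 mg as a reason for using that regimen.

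**Follow-up.** SAP 5.13 says: "Follow-up data is defined as all data occurring up to 30 days (planned maximum follow-up time) after last dose of treatment including rescue". SAP 5.13.2 says: "The analysis period is defined as the treatment period plus 30 days off-drug follow-up time". Against this, SAP 4.1 has a "Post-Treatment Follow-Up Period, spanning approximately 8 weeks from Week 52 (Visit 17) to Week 60 (Visit 801", the protocol Synopsis also plans 8 weeks, and SAP 5.2.2 says: "Postbaseline measurements are collected after study drug administration through Week 60 (Visit 801) or early discontinuation visit". In SAP 5.13, "by-visit summaries will include planned on-treatment visits" unless otherwise specified, and the optional follow-up statistics describe "the last measure observed during post-treatment follow-up (up to 30 days after the last dose of treatment including rescue".

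**The concern.** After induction, the Week 0 arm no longer tells what a subject receives. Under Protocol 5.1, placebo nonresponders go to 300 mg, active responders are re-randomized 2:1 to stay on drug or receive placebo, and 50-mg and 150-mg nonresponders move to a higher dose. If maintenance safety columns follow the Week 0 product, the placebo column consists largely of subjects on active drug, active columns contain subjects on placebo, and the 300-mg data that the design sets out to collect have no column.

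The follow-up wording raises a smaller question. Visit 801 is the only scheduled visit after the Week 52 dose. A window described as the planned maximum, but shorter than the planned follow-up, leaves that visit's measurements out of the main safety summaries by default.

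**Working it through.** **Does another rule settle the grouping?** SAP 5.2.1 says assigned, but SAP 4.2 uses assignment for the Week 0 randomization, so the word does not point clearly to the current regimen. SAP 5.2.2.2 mentions reassignment to active treatment, but only for an optional baseline. The gap remains.

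**Size of the mismatch when maintenance starts.** Inputs: 50 subjects per arm (Protocol 10) and the reassignment rules (Protocol 5.1, SAP 4.1). Let r be the EASI-50 rate in an arm, with no dropout. The documents give no EASI-50 rates; I assume 20% to 40% for placebo and 40% to 70% for active arms.

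| Week 0 column | Not on the column's regimen | Result, of 50 |
|---|---|---|
| Placebo | 1 − r, all on 300 mg | r = 0.2: 40; r = 0.4: 30 |
| 50 mg, 150 mg (each) | 1 − 2r/3 | r = 0.4: 36.7; r = 0.7: 26.7 |
| 600 mg | r/3, all on placebo | r = 0.4: 6.7; r = 0.7: 11.7 |

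For 50 mg and 150 mg, 1 − 2r/3 is smallest at r = 1, where it is 1/3. So at least one third of each column is expected to be off its regimen at any response rate. This bound holds under either document's rule for 150-mg nonresponders. The two components are dose increases, 1 − r (30 of 36.7 at r = 0.4; 15 of 26.7 at r = 0.7), and placebo, r/3 (6.7 and 11.7). At the assumed rates, most of the mismatch is therefore dose increase.

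**Follow-up length.** The stated figure of 30 days cannot be reproduced from the Schedule of Activities (Protocol 2). The last injection is at Visit 17, Day 364 (±4), and Visit 801 is Day 420 (±5).

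- Planned gap: 420 − 364 = 56 days.
- Shortest with windows: 415 − 368 = 47 days. Longest: 425 − 360 = 65 days.
- Visit 801 falls 47 − 30 = 17 to 65 − 30 = 35 days after the window closes.
- Planned follow-up outside the window: (56 − 30)/56 = 46%.

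**What is left out for subjects dosed at Week 52.** By default, Visit 801 laboratory and vital-sign values and adverse events starting after Day 30 do not enter the event and shift tables. By-visit summaries do not recover the measurements, and the optional follow-up statistics also stop at 30 days, before any follow-up visit is due. The window runs from the last treatment including rescue, so later rescue use can extend it.

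**What is kept.** Adverse events with onset by Day 30 (even if recorded at Visit 801), deaths, malignancies, full listings (SAP 5.13) and registry serious adverse events (SAP 5.18) are kept. This takes the 30-day definition at face value. The further TEAE condition in SAP 5.13.2, "on or prior to the last visit date during the analysis period", is unclear when no visit is scheduled in those 30 days.

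**The case against.** A 30-day off-drug window can be a deliberate choice; SAP 5.13.2 repeats it without calling it a maximum. That stands. What is contradicted is the description of 30 days as the planned maximum, and the consequence for Visit 801 is modest.

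The large percentages for the 50-mg and 150-mg columns come mainly from active subjects moving to a higher active dose, and withdrawn responders restart their induction regimen on loss of response. That also stands. The serious mixing of drug and placebo is in the placebo column.

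Four stronger readings are tempting but not supported:

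- *Visit 801 drops out of the safety analysis.* It does not, given the data kept as listed above.
- *The 30-day cut costs maintenance a urinalysis and leaves late dosing untested.* Visit 801 belongs to Period 4. After the Week 16 baseline, the schedule has one maintenance urinalysis, at Week 32. None is scheduled from then to Week 52, so the gap comes from the schedule and no choice of window would fill it.
- *The Fisher test in the maintenance shift-to-low table simply departs from the protocol.* Protocol 10.2.1.2 allows only descriptive statistics in maintenance, but Protocol 10.2.1 plans Fisher's test for categorical safety data with no period limit. The conflict is also within the protocol.
- *The window should run from the last study-drug dose and ignore rescue.* That could shorten it for subjects using rescue after their last injection, so it would lose data.

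**Conclusion.** The grouping point holds and should be fixed before maintenance safety tables are programmed. Read literally, SAP 5.13 shows all placebo nonresponders as placebo while they receive 300 mg, and shows one third of active responders as active while they receive placebo, until they restart. The 30 to 40 of 50 placebo subjects rest on the assumed 20% to 40% response with no dropout. The one-third lower bound for the 50-mg and 150-mg columns needs no response-rate assumption, only no dropout. All these counts describe the start of maintenance and will change as subjects lose response. Tables confined to induction are unaffected.

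The follow-up point also holds but is minor: 30 days is not the planned maximum, since the plan is 56 days (47 to 65 with windows).

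**What to change.** 1. In SAP 5.13, limit Week 0 grouping to induction. For maintenance, summarize by the regimen in force at onset or measurement, with 300-mg and withdrawn-to-placebo columns and exposure time. Align 5.2.1 and 5.13.1 to 5.13.6, state the period of each adverse event table, and state the change from Protocol 10.1 and 10.2.1.
2. Correct the planned-maximum wording. Keep the 30-day tables as an explicit on-treatment-plus-30-day analysis, add one event and laboratory summary through Visit 801, and clarify the last-visit clause in 5.13.2.
3. Reconcile the start of maintenance (Week 16 in Protocol 5.1 and SAP 5.2.1 and 5.2.2.2; Week 20 in SAP 4.1) and the two statements of where 150-mg nonresponders go (Protocol 5.1 and SAP 4.1). These set the period boundary and who is in the 300-mg column. Reconcile the use of Fisher's test in maintenance safety tables (Protocol 10.2.1 and SAP 5.13.3 against Protocol 10.2.1.2).

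**Cost.** SAP wording, a regimen-at-onset flag (dose times are already recorded, Protocol 7.2.1), extra columns and one added summary. Under Protocol 10.2.1, an amendment is needed only if a principal feature changes; otherwise the change is justified in the study report.

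**Downsides.** Maintenance columns are not all randomized groups. Early events in the withdrawn-to-placebo column occur with residual drug: with a Week 16 switch, the last active dose is at Week 12, and at the 24-day half-life (Protocol 3.2, simple exponential decline) 0.5^(28/24) = 45% of it remains at Week 16 and 0.5^(56/24) = 20% at Week 20. Events after Day 30 are less clearly attributable to drug.
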